### **Aim 1**: To determine the Neurobiology of Exercise and Biological CVD risk factors:

- (1A) *Body-to-Brain hypothesis*: Exercise-induced changes in peripheral markers of CVD risk (i.e., insulin resistance, pulse wave velocity, CRF, oxidative stress, biomarkers of endothelial function) will precede and partly explain (statistically mediate) exercise-induced changes in functional and structural features of some areas within visceral control circuits (prefrontal cortex [PFC], anterior cingulate cortex [ACC], insula, hippocampus, and amygdala).
- (1B) Brain-to-Body hypothesis: Exercise-induced changes in functional and structural features of some areas within visceral control circuits precede and partly explain (statistically mediate) consequent changes in peripheral autonomic and neuroendocrine mediators of CVD risk that are under neural regulation, including baroreflex sensitivity, heart rate variability, glucocorticoid control.

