
sufficiently powered to test our hypotheses using structural equation modeling even after attrition. In sum, our planned sample size of 150 (N=75 per group) will be sufficient for allowing us to test our primary hypotheses.

**1.4.2. PRELIMINARY STEPS**: Prior to hypothesis testing, all data will be examined to determine: 1) frequency distributions for missing data and out-of-range values; 2) normality and internal consistency of subscales; and, 3) association between variables that may be highly correlated to guard against multicolinearity, which would inflate standard errors and make estimation

[figure not shown]

Figure 1. Diagram of exemplar full longitudinal mediational model. Paths involved in estimating longitudinal stability and residualized change are in black, paths involved in mediation are in red, and non-essential parameters are grayed out for legibility.

unstable. We will also examine the distribution of factors between groups to assess whether covariate-adjustment is required. Missing data: All outcomes will be tested using an intent-totreat (ITT) framework. Sensitivity will be explored using adherence to the intervention (e.g., per protocol). We will report reasons for dropouts and explore missing data mechanisms. To examine whether missingness is unrelated to other observed and unobserved measurements (missing completely at random, MCAR) or to the observed measurements only (missing at random, MAR), testing for completely random dropouts will be carried out. Additional sensitivity analyses test for informative dropouts. We will apply pattern-

mixture models by stratifying our data by dropout patterns and fitting separate regression models to strata.

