**1.4.3 MEDIATION:** Aim 1 has two hypotheses, (a) to test whether the peripheral effects of exercise mediate brain effects, and (b) whether the effects of exercise on the brain mediate the beneficial effects of exercise on peripheral mediators of CVD risk. We propose to test these hypotheses using longitudinal mediation models in a structural equation modeling (SEM) framework. Aim 1A: In this model, the exercise groups (X) are proposed to influence visceral control circuits (Y) via changes in peripheral pathways (M) including insulin resistance, oxidative stress, endothelial dysfunction, and CRF. We will first examine whether brain or these peripheral CVD pathways can be summarized as latent variables to control for measurement error. When using latent variables, the modeling will proceed by first establishing well-fitting measurement models, and testing for measurement invariance across waves. To test the hypothesis proposed in Aim 1A, analyses will be conducted both on a voxel-wise basis (e.g., using the BRAVO Toolbox (https://sites.google.com/site/bravotoolbox/)) or using extracted data from SPM, FSL, or FreeSurfer, depending on the imaging modality and analysis. In the latter case, we will use a theory-driven approach by selecting values from anatomical or functionally-defined regions-of-interest (ROI) on visceral control regions. Each imaging modality will be analyzed in separate models unless we have a theoretical or empirical basis for including multiple imaging metrics in a single model. We will use standard cluster-based and FDR corrections for multiple comparisons for all voxel-wise analyses and the Brain Connectivity Toolbox for graph theory metrics (i.e., segregation). Although directional hypotheses have been posited for our mediation analyses, a more conservative significance will be set at .01 to limit inflation of type 1 error. Global and incremental model fit will be verified using multiple fit-indices (chi-square, RMSEA, CFI, TLI, SRMR). With three waves of data, we will use full longitudinal mediation to test our hypotheses. Full longitudinal mediation allows us to test the effect of initial standing on the hypothesized predictor (X – Exercise group) at T1 on change in the mediator (M – peripheral CVD markers) from T1 to T2, controlling for initial standing on M, and the effect of the mediator (M– peripheral CVD measures) at T2 on the change in the outcome (Y – change in brain measure) from T2 to T3, controlling for initial value of the outcome. Mediation will be tested by calculating the indirect effect of paths that are consistent with longitudinal mediation (i.e., paths a and b in Fig. 1). Here the estimate a\*b provides a measure of the longitudinal mediated effect because it represents the effect of X at T1 on residualized change in M (path a), and M at T2

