
on residualized change in Y (path b). Significance of the mediation (i.e., indirect) effect will be examined using techniques that account for non-normality in the parameter distribution, namely bias corrected bootstrapping-based approaches. A benefit of full longitudinal mediation models is that the direction of the paths can be reversed (Y->M->X) to test for the opposite causal direction, and bidirectional effects can similarly be tested. We will test for these possibilities by comparing models with paths reversed and allowing bi-directional effects. Finally, we aim to explore the role of other potential mediators (i.e., sleep) and moderators (e.g., gender) on the direction and strength of associations. Aim 1B: We will proceed with similar approaches described above for Aim 1A including using a voxel-wise approach and a theory-driven approach by selecting anatomical or functionallydefined ROIs on visceral control circuits or the white matter pathways that connect them. Importantly, there may be regional dissociations between the brain regions identified in Aim 1A and those identified in Aim 1B. Using voxel-wise analyses, we will be able to adjudicate the regional specificity or overlap between the regions identified in Aim 1A with those of Aim 1B. Using these procedures, we will also be able to determine the specificity of particular effects (e.g., regions associated with BRS but not with HRV) or differences across imaging metrics (e.g., differences of effect between functional connectivity, cortical thickness, white matter). With three waves of data, we will use full longitudinal mediation to test our hypotheses that X (Exercise group) influences BRS, HRV, and glucocorticoid control (Y) via its effects on brain plasticity on visceral control circuits (M). The description of the SEM modeling approach for Aim 1A will be applied to test mediation for Aim 1B. To test Aim 2A & B: The analytical plans for testing Aim 2A and 2B along the lines depicted in the heuristic model of Figure 1 will proceed like that described above for Aim 1A and B. That is, we will test how the effect of the hypothesized predictor (X – Exercise group) influences the change in the mediator (M – visceral control circuits), on stress reactivity and affect metrics that are measured in Projects 1-2 (e.g., EMA and ABP measures identical to those used in NOAH). Similar to Aim 1, we will be able to model opposite causal directions and bidirectional effects by reversing the paths in the model and will be able to determine specificity of particular effects (e.g., regions associated with emotion regulation, but not daily life stress reactivity) or differences across imaging metrics (e.g., differences of effect between functional connectivity, cortical thickness, white matter). As above, we will also test other potential mediators (i.e., sleep) and moderators (e.g., gender) on the direction and strength of associations.

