#### 1.6 **RANDOMIZATION**:

After the completion of the baseline measures and sessions described above the participants will be randomly assigned to one of two groups. These include (a) an exercise condition that will consist of 150 minutes per week of moderate-to-vigorous intensity exercise, or (b) a PA and health information group. We will use a computer randomization protocol that will incorporate a verification that all session visits have been completed and data entered into the database. We will use a minimization algorithm with equal allocation to one of the two groups. The use of the minimization strategy will ensure treatment balance on the two factors of age at study entry (=<42, >42) and gender. Once randomized, an assigned staff member will contact the participant via phone with the group information. On this contact, the staff member will give information such as date, day, time, and location of the subject's first intervention session.

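### The reversed model for Aim 1A is written with the randomised group as the final outcome; its last path cannot be estimated, and the order is not the brain-first rival

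*Combined protocol and SAP*

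**What the plan says.** In section 1.4.3 MEDIATION of the combined protocol and SAP, the Aim 1A symbols are fixed by this sentence: "the exercise groups (X) are proposed to influence visceral control circuits (Y) via changes in peripheral pathways (M", where M covers insulin resistance, oxidative stress, endothelial dysfunction and fitness. The indirect effect is a*b. Path a is the effect of X at T1 on residualised change in M. Path b is the effect of M at T2 "on residualized change in Y (path b").

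The same section then says that "the direction of the paths can be reversed (Y->M->X) to test for the opposite causal direction", and commits to comparing models with reversed paths and models with bidirectional effects. Aim 2 promises to reverse the paths in the same way but does not write the order out.

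Section 1.6 RANDOMIZATION states that, once baseline is complete, "the participants will be randomly assigned to one of two groups". Allocation is by minimisation on age and gender. No later re-assignment is described.

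The hypothesis being checked is in the Summary: peripheral changes "will precede and partly explain (statistically mediate) exercise-induced changes in functional and structural features of some areas within visceral control circuits". Aim 1B puts the brain first, for "peripheral autonomic and neuroendocrine mediators of CVD risk that are under neural regulation, including baroreflex sensitivity, heart rate variability, glucocorticoid control". For the mediation tests, "a more conservative significance will be set at .01". The section headed Amendments in Study Protocol reduces the target to 120 and makes the mediation analyses exploratory.

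**The concern.** Aim 1A is a claim about order: periphery first, brain second. The reversed model is the plan's stated check on the opposite order. Read with the plan's own symbols, it runs from brain to periphery to randomised group. Neither brain nor peripheral values can cause group, because allocation uses only age and gender. The alternative that would challenge Aim 1A is that exercise changes the brain first and the brain then changes the periphery. That is X->Y->M, a different model.

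At stake is whether the trial can say anything about the competing direction for Aim 1A's own markers. An analyst following the text would meet a model that cannot be fitted and would have to improvise a replacement after seeing the data.

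**Working it through.** The plan states no figure for the reversed model, so there is none to reproduce. The check applies the plan's definition to the order it writes.

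**Step 1. Forward model, as defined in 1.4.3 MEDIATION.**
- Path a: M2 = s·M1 + a·X + error
- Path b: Y3 = s·Y2 + b·M2 + error (other terms omitted)

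Both outcomes vary after conditioning on their earlier value, so both paths are estimable.

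**Step 2. The same definition applied to Y->M->X.**
- First path: M2 = s·M1 + a'·Y1 + error. This is estimable.
- Last path: X3 = g·X2 + b'·M2 + error.

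Group is assigned once, so X3 = X2 for every participant. The solution is g = 1 and b' = 0 with no residual, so Var(X3 | X2) = 0. Numerically, regressing X3 on X2 and M2 in a simulated trial gave a coefficient of 1 on X2, 0 on M2 (to rounding error), R² = 1 and a residual sum of squares of about 0. The covariance matrix of X over the three waves has rank 1. None of this depends on an assumed effect size.

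**Step 3. The written order against the rival.**

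| Model | First link | Second link |
|---|---|---|
| As written, Y->M->X | Y->M | M->X |
| Brain-first rival, X->Y->M | X->Y | Y->M |

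They share only the Y->M link. The written model never estimates X->Y, the effect of exercise on the brain that the rival needs.

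**Step 4. The rival with X first.**
- Y2 = s·Y1 + a·X + error
- M3 = s·M2 + b·Y2 + error

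Both paths are estimable. In 1,000 simulated trials at each of n = 120 and n = 96 (120 × 0.8, the amended target less 20% attrition), with only the forward Aim 1A pathway true, the path X->Y2 given Y1 was significant at .01 in 0.8% of runs at both sizes. That is close to the nominal 1%.

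**Step 5. Would the bidirectional model serve?** This step is an illustration. Assumed, because the documents give no values: b = 0.3; stability s = 0.6 or 0.7; residual SD √(1 − s²); a = 0.3, 0.5 or 0.6; n = 96; both paths required to be significant at .01. With the brain-first pathway true:

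| a | X->Y2->M3 alone | Same effect in a bidirectional model, X exogenous |
|---|---|---|
| 0.3 | 18–26% | 18–25% |
| 0.5 | 53–70% | 53–70% |
| 0.6 | 68–82% | 67–82% |

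The two detect the rival equally well. A bidirectional model with X first and both cross-lags would therefore be an adequate replacement, if that is what the plan means.

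**The case against.** **The notation is shorthand.** The parenthesis sits in a sentence about a general advantage of the method, and everywhere else X is the predictor. The authors may have meant only to reverse the link between M and Y. That is plausible. But it is the only order written for the Aim 1A reversal, it uses symbols just defined, and Aim 2 refers back to it.

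**The bidirectional models cover the rival.** They can, as step 5 shows, and this is the strongest reply. It holds only if X is exogenous and both cross-lags are present, and the text lists neither condition. Figure 1 is not shown in the copy reviewed and may help. Its caption says that "paths involved in mediation are in red, and non-essential parameters are grayed out for legibility" but mentions no reversed model. The missing figure is not held against the plan.

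**Aim 1B is already brain-first.** This stands in part. The Summary introduces its markers with the word including, and 1.4.3 MEDIATION opens by describing the hypothesis broadly. The markers named are nevertheless not Aim 1A's.

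**The written model is not blind to the opposite direction.** This is correct. Its first path, Y1 on change in M, is estimable. With the assumptions of step 5 and the brain-first pathway true, it is significant at .01 in about 82–92% of simulated trials. It shows that brain precedes periphery, but not that an exercise effect passes through the brain.

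**A stronger reading to resist.** A reader might infer that the reversed model will produce false evidence of mediation through the brain. If lagged X is dropped and group is regressed on M2, a simulation with X->M and Y->M but no X->Y does give significant results in 9–80% of trials, depending on assumed path sizes and adjustment. No section describes that fit, so these are not the plan's error rates. Such a result would also read as brain to periphery to group, which is visibly impossible under randomisation. It would become a claim about the brain as mediator only if someone relabelled it.

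**Conclusion.** The point holds as a specification error. With group last, the final path of the reversed Aim 1A model has zero outcome variance under the plan's own definition, and the written order is not the brain-first rival. This rests on two things in the documents: the definition of path b as residualised change, and a single assignment after baseline. It needs no assumed effect size.

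The severity is minor. The error is confined to the directionality check for Aim 1A, with an unclear carry-over to Aim 2, inside analyses that are now exploratory. A failure to fit would be obvious rather than silent, and the bidirectional models may already supply what is needed. The documents do not support the inference that the forward Aim 1A model, Aim 1B's stated model or the primary mixed-model outcomes are compromised, or that Aim 1A is favoured by design. Confidence is medium, because the intended bidirectional paths cannot be seen.

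**What to change.** In 1.4.3 MEDIATION:

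1. Replace the parenthesised order Y->M->X with X->Y(T2)->M(T3).
2. State that X is exogenous in every reversed and bidirectional model.
3. State that the bidirectional model includes both the M->Y and the Y->M cross-lags.
4. Name the comparison: the indirect effect X->M2->Y3 against X->Y2->M3.
5. Apply the same definition where Aim 2 speaks of reversing the paths.

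If the authors already intended this, the edit simply records it. The cost is SAP wording only, with the same data and the same software.

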
#### 1.5 PROCEDURES:

Before the collection of baseline data, all staff will have had ethics training and appropriate certification of research training modules.

#### 1.5.1 SCREENING:

During the UCSR telephone screening interview, numerous medical history questions will be asked to verify that the potential participant meets inclusion criteria as no medical record retrieval is being used. Information about safety to exercise will be obtained over the phone (i.e., history of falls) to ensure that

exercise will not be dangerous for the participant. Once deemed eligible, this participant's contact information will be sent to an eBACH staff member who will conduct a secondary screen specifically for physical activity and MRI safety eligibility. Information about the participant's current exercise status will be collected and participants that engage in more than 75 minutes of structured exercise per week will be considered ineligible. Information regarding metal in the body for MRI safety will obtained, including information about any metallic objects in their body. If a participant is deemed unsafe to exercise based on the physical activity readiness questionnaire, the participant will be required to have prior approval by their primary care physician before being admitted into the exercise program.

#### 1.5.2 INCLUSION AND EXCLUSION CRITERIA:

#### **Inclusion Criteria:**

- **Age** individuals aged 28-56 years old when signing the consent form.
- **Gender & Ethnicity** men and women are both eligible to participate. We expect the study population to be approximately 50% women. All ethnic groups are eligible for the study. We expect the study population to be approximately 30% minorities.
- Ambulation study participants must be able to walk without pain or use of an assisted walking device. This will be determined during the initial phone screen. Ambulation will also be assessed in person as the potential subject must be able to complete the VO2 Max test on a treadmill.
- Physical Activity and Fitness Level all participants must report engaging in less than 75 minutes per week of exercise and have a VO2max percentile less than 75 based on the ACSM Guidelines for Exercise Testing (10th edition).
- Residency Since the intervention is 12 months in duration, all potential participants must reside in the Pittsburgh area and plan on residing in the area for at least one year after randomization. It is recommended that the study coordinator during the second screen assess potential participants' distance from the exercising sites since the study requires 2 visits per week. The further a participant is from an intervention site, the higher the probability is for the person to be unable to adhere to the protocol.
- **Reliable transportation:** Participants must have reliable transportation to complete the outcome measures and the intervention requirements.
- Willingness to be randomized To be eligible, all potential study participants must be willing to be randomized to either of the intervention arms. Individuals that insist on participating only if they can choose which arm they belong to should not be enrolled.

#### **Exclusion Criteria:**

#### Medication Use:

- A. Reported use of the following medications on one or more occasions in the past 14 days constitutes grounds for exclusion:
  - 1. Antihypertensive or cardiac medications (diuretics, beta blockers, calcium channel blockers, ACE inhibitor/ARB, cardiac glycosides, central sympatholytic HTN drugs, antiarrhythmic drugs, vasodilator drugs, other cardiac drugs).
  - 2. Anticonvulsant medications
  - 3. Antiparkinson medications
  - 4. Protease inhibitors or other Anti-HIV medications
  - 5. Medications for the treatment of mania
  - 6. All other centrally active or psychotropic medications excluding anti-anxiety, antidepressant, or antipsychotic/tranquilizer medications.
  - 7. Insulin
  - 8. Chemotherapy
  - 9. Immunosuppressants and related biological agents (Imuran, methotrexate, and cyclophosphamide)
  - 10. Prescription weight loss medications and ephedrine OTC
- B. Reported use of the following medications on a "regular" basis is grounds for exclusion. For this purpose, "regular use" is defined as reporting that the prescribed medication was taken 7 or more days in the past 14 days. Individuals who take these medications, but less frequently than 7 out of the past 14 days are not excluded:
  - 1. Anti-anxiety medications (Ativan, valium, Xanax)
  - 2. Sleep medications (e.g., trazadone at bedtime for sleep)
  - 3. Asthma oral medications
  - 4. Asthma/allergy inhalants (alupent, albuterol)
  - 5. Anti-depressant medications
  - 6. Antipsychotic/tranquilizer medications
  - 7. Glucocorticoids (oral; prednisone, cortisol)
  - 8. Medical marijuana
- C. Reported use of more than 2 non-insulin medications for diabetes on a "regular" basis is grounds for exclusion. For this purpose, reported use of combination medications, involving two or more non-insulin medications for diabetes in a single pill, is counted as 2 separate medications and would be grounds for exclusion.
- D. A person who reports that he or she was once on a disallowed medication, but has discontinued this medication for at least a month or longer and is otherwise eligible, is allowed to participate in the study.
- Substance use exclusions:
  - A. Anyone reporting 35 or more alcoholic drinks in the last 7 days is excluded.

- B. Anyone reporting consumption of 6 or more alcoholic drinks on 3 or more occasions in the past 7 days is excluded.
- C. Anyone reporting a score of 8 or more on the 10-item AUDIT scale (indicating harmful or hazardous use of alcohol) is excluded.
- D. Anyone reporting use of illicit drugs on 7 or more days in the past 2 weeks is excluded.
- Medical conditions that are disallowed are:
  - A. Self-reported prior heart attack, stroke, bypass surgery, angioplasty, congestive heart failure, arrhythmia (cardiac rhythm problems).
  - B. Hypertension (SBP/DBP  $\geq$  160/and/or  $\geq$ 100 mmHg).
  - C. Cancer (treatment in last 12 months, allowance for non-melanoma skin cancer) potential participants who have received treatment in the last 12 months for cancer, including radiation or chemotherapy will be excluded from the study.
  - D. Liver disease any person who has had hepatitis B or C, liver failure or Cirrhosis will be excluded from the study.
  - E. Kidney disease potential participants who indicated they have chronic kidney failure, have undergone dialysis, or have had a kidney transplant will not be eligible to participate.
  - F. Type I diabetes or insulin dependent Type II diabetes Type 2 diabetics if they are taking insulin or 3 or more diabetes medications. Single injections that contain 2+ drugs count as 2 medications.
  - G. Self-reported history of a major neurological disorder or brain injury resulting in ongoing symptoms or cognitive impairment (e.g., multiple sclerosis, cerebral palsy, major head injury)
  - H. Self-reported chronic psychotic illness (schizophrenia, bipolar disorder).
  - I. Lung disease requiring drug treatment (asthma or allergy inhalers are not exclusionary unless they are used on a "regular basis")
  - J. Weight loss surgery within the past 5 years.
- Other exclusionary criteria:
  - A. Current pregnancy or plans to become pregnant over the next year any woman who is pregnant via a pregnancy test at the baseline visit will be excluded from the study. A pregnancy test will also be given at the MRI visit and this will be repeated at 6-months and 12-months.
  - B. Those who make regular use of an assistive walking device are excluded.
  - C. Those who are not fluent in English are excluded (defined as having spoken and read English every day for <10 years).
  - D. Those with a visual impairment that would prevent them from reading printed text or text on a computer screen, iPad, or other electronic device are excluded.

- E. Those with color blindness, who may not be able to distinguish colors on some of the tasks used in this study, are excluded.
- F. Those who have claustrophobia (fear of enclosed or confined spaces) are excluded.
- G. Those who have medical devices, implants or other metal objects in or on the body that cannot be removed and are incompatible with use of fMRI (for example, tattooed eyeliner) are excluded.
- H. Those who are unable to fit into an MRI scanner are excluded.
- I. Those who report working the night shift on a frequent basis (half or more of the hours worked in a full workday are between midnight and 8 am, and this has occurred more than 12 times during the past year) are excluded.
- J. Those without reliable access to a telephone throughout the day (home, work, or cell phone) are excluded.
- K. Those who are otherwise unable to meet the requirements of the study (for example, persons whose employment or personal situation will not permit momentary interruptions required for electronic diary and ambulatory data collection) are excluded.
- L. Those unwilling to be randomized to one of the two groups will be excluded.
- M. Individuals that self-report engaging in 75 minutes or more of structured physical activity per week will be excluded. This will be determined using a combination of questionnaire and interrogation by trained exercise staff.
- N. Those that have cardiorespiratory fitness levels that are above the 75%ile based on ACSM criteria will be excluded.

